An additional component of the study, which is entirely optional, is to obtain patient serum samples (about two teaspoons) in the operating room and 15 minutes and 4 hours after ketamine infusion. We will use these samples to assess levels of IL-1, IL-6, TNF- α , and BDNF, which are markers for pain. In addition, with patient consent, we will also store serum samples for future research use to measure other cytokines and neurotrophic factors and molecular markers associated with pain and depression.

Study site: Tisch Hospital

Outcome measures

Primary outcome measure: scores on the following questionnaires: 1) The Beck Depression Inventory (BDI); 2) Visual Analog Scale (VAS) score; 3) McGill's short form; 4) QoR-15 form; and 5) Montgomery-Asberg Depression Rating Scale (MADRS). The BDI and MADRS provide assessments for mood and function, VAS and McGill's assess pain, and QoR-15 assesses patient's overall satisfaction with postoperative recovery.

After consent is achieved in the pre-admission clinic prior to surgery, patients will be asked to fill out BDI, MADRS and QoR-15 forms to establish baseline scores. The BDI, MADRS will be filled out on postoperative days (POD) 0 after the infusion of ketamine, and BDI, MADRS and QoR-15 forms will be repeated on POD1, 2 and 7. McGill's short form will be filled out prior to discharge from the PACU and on POD 1, 2 and 7. VAS will be filled prior to PACU discharge, and every day while patient is in the hospital and on POD 7. VAS is a routine part of hospital care and will be administered daily whether a patient is enrolled in the study or not. If a patient has been discharged prior to POD2 or 7 (patients typically are discharged on POD2 or 3 in our practice), then a member of the study team will contact the patient by telephone to fill out these questionnaires.

Secondary outcome measures: 1) length of stay during hospitalization; 2) opioid usage per hour during the PACU stay before and after ketamine infusion; 3) opioid usage per day throughout the hospital stay; 4) time to out of bed to chair (OOB); 5) spirometry use 4 hours after the termination of ketamine infusion; 5) anti-emetic use in the PACU.

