Protection of Human Subjects: Patients who will undergo bariatric surgery who meet entry criteria will be presented the option of enrolling in proposed studies. If they decide to participate, they will be asked to provide written informed consent prior to participation in this study. They will review an IRB-approved research consent with study personnel. This consent form will describe the purpose of the study and how long it will last, the procedures to be used, any expected discomfort or inconvenience, the expected risks and benefits, alternative treatment plans, use of research results, and any special circumstances. The consent form will be read and signed in the presence of a member of the research team. Study subjects will be given the opportunity to ask questions at the time of signing consent and throughout the course of the study. They will also be informed of their rights as study participants, that they are free to choose not to participate and can withdraw at any time. A copy of the consent will be given to all study participants. If they have questions or concerns at a later time, they may use the phone numbers listed on the consent form to contact the investigator or other study associates.

Institutional Review Boards: The principal investigator will ensure that a duly constituted Institutional Review Board (IRB) complying with all Federal regulations will review all protocols and informed consent forms. The investigator will promptly report to the IRB all changes in research activity and all serious adverse events or unanticipated problems involving risks to human subjects or others. No changes will be made to protocols without IRB approval, except where necessary to eliminate immediate hazards to human subjects. If an emergency change is necessary, the IRB will be notified within 24 working hours. The NYU School of Medicine IRB operates under OHRP Federal-Wide Assurance of compliance number FWA00004952.

Patient Confidentiality: To maintain patient confidentiality, all laboratory specimens, evaluation forms, reports and other records will be identified by a coded number only, and HIPAA guidelines will be followed. Clinical information will not be released without the written permission of the patient, except as necessary for monitoring by the NYU IRB. Subjects will be

informed of these exceptions in the informed consent document

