Sample Size Justification: Previous studies on the antidepressant effects of ketamine on depressed patients typically yield a mean difference in psychometric measures of 40%, with a standard deviation of roughly 40% as well. Power analysis yields $n = 50$ patients in each arm. This will allow for us to detect a true difference in the mean value of our outcome variable of $\pm 22.5\%$ with a probability (power) of 0.8. The type I error probability associated with this test of the null hypothesis that the population means of the ketamine versus control groups are equal is 0.05.

Statistical Analysis: For this study, descriptive statistics will be performed for all data and subgroups as needed:

- 1) Outcome tests (see above), N (%) for each category, showing absolute values, absolute

and percent differences, stratified by treatment etc.

- 2) Demographics showing continuous parameters (age, height, weight, etc.) as mean + SD; categorical parameters, as N (%); all also stratified by treatment.

Analysis of variance (ANOVA) test with repeated measures will be performed to determine within-patient effects (time) and between patient effects (treatment) on outcome measures. Pearson correlation will be used to assess relationships between continuous variables, and Spearman's Rho will be used for ranked data. For non-normally distributed, the Kruskal-Wallis test will be used for global significance, and Mann Whitney for subsequent pairwise comparisons.

Exploratory analysis will fit continuous (VAS score, length of stay in the hospital) and categorical (ordinal outcome data) to a Logistic Regression model which predicts the treatment bivariate (IV ketamine or placebo).

Interim Data analysis: An interim data analysis will be performed after a total of 50 patients have completed the study. An analysis of primary and secondary endpoints will be analyzed, and if the primary endpoints are met, we will opt to terminate the study.

DATA SAFETY AND MONITORING PLAN

Timeline

- 1) Estimated start date: Sept 1, 2013
- 2) Estimated time for start-up: 2 months
- 3) Time allotted for enrollment: 2 years
- 4) Estimated study end date: August 30, 2015

Data acquisition and management

The research material obtained from human subjects in this proposed study will be collected solely for research purposes. It will be as follows:

- a. *Clinical information* obtained by medical history, questionnaires and interviews.

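### The repeated-measures ANOVA for the questionnaires comes with no analysis set or missing-data rule; in its standard form one missed POD7 call removes a dosed patient's POD0–2 scores from that comparison

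*Combined protocol and SAP*

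**What the plan says.** The Statistical Analysis section, repeated within the Data Safety and Monitoring Plan, names one longitudinal method for the outcome measures: "Analysis of variance (ANOVA) test with repeated measures will be performed to determine within-patient effects (time) and between patient effects (treatment". For non-normal data, "the Kruskal-Wallis test will be used for global significance, and Mann Whitney for subsequent pairwise comparisons". Neither place defines an analysis population, an intention-to-treat rule, imputation, a mixed model or a sensitivity analysis for missing scores, and no other section does.

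On the schedule, Outcome measures asks for BDI and MADRS at baseline and on POD0, and then "BDI, MADRS and QoR-15 forms will be repeated on POD1, 2 and 7". If the patient has left hospital before POD2 or POD7, "a member of the study team will contact the patient by telephone to fill out these questionnaires". The same paragraph notes that "patients typically are discharged on POD2 or 3 in our practice".

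On loss, the Protection of Human Subjects paragraph tells patients that "they are free to choose not to participate and can withdraw at any time". Nothing says whether scores already collected are kept. Overall study design and plan lets the randomisation list be extended for screening failures, not for patients lost after dosing. Retention is summarised in the DSMB report, which does not touch the analysis.

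**The concern.** Conventional repeated-measures ANOVA needs a value at every level of the time factor. A patient who was dosed and scored on POD0, 1 and 2 but not reached on POD7 drops out of that questionnaire's ANOVA altogether. POD7 is the systematic exposure, because almost every patient is at home by then. POD2 is by telephone only for patients already discharged.

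Two things are at stake. The first is precision: scores in hand go unused, and the sample size carries no allowance for loss. The second is the comparison itself. If being reachable on POD7 depends on how the patient feels, the analysed patients are no longer the randomised arms. The Background describes the antidepressant effect of ketamine as rapid in onset and lasting up to seven days, so the POD0–2 scores are central to Aim 1.

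**Working it through.** **Inputs from the documents.** 50 per arm; SD 40%; detectable difference 22.5%; power 0.80; type I error 0.05 (Sample Size Justification). BDI and MADRS have four post-infusion scores: POD0, 1, 2 and 7 (Outcome measures).

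**Inputs assumed.** The documents give no loss rate and no correlation between visits. The checks use a correlation of 0.6 between any two visits, loss of the POD7 score only, and the loss rates shown.

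**1. The plan's own figure.** n per arm = 2 × (1.960 + 0.842)² × 40² / 22.5² = 49.6, so 50. Power at 50 per arm is 0.803. The stated size reproduces, two-sided, with no reserve for incomplete patients.

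**2. Power if incomplete patients are deleted,** in that same two-mean calculation, Φ(22.5 / (40 × √(2/n)) − 1.960):

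| Assumed loss | n per arm | Power |
|---|---|---|
| 0% | 50 | 0.803 |
| 10% | 45 | 0.761 |
| 20% | 40 | 0.711 |
| 30% | 35 | 0.653 |

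**3. Standard error with 15% of POD7 scores lost at random.** The outcome is the patient's mean of four scores.
- Variance of that mean: 1600 × (1 + 3 × 0.6) / 4 = 1120.
- Nothing missing: √(2 × 1120 / 50) = 6.69.
- Deletion, 50 × 0.85 = 42.5 per arm: √(2 × 1120 / 42.5) = 7.26.
- All scores: only the part of POD7 that the earlier three scores do not predict is lost. The mean of those three has variance 1600 × (1 + 2 × 0.6) / 3 = 1173.3, and its covariance with POD7 is 0.6 × 1600 = 960. The residual variance is 1600 − 960² / 1173.3 = 814.5. POD7 has weight 1/4 in the mean, so the part affected is 814.5 / 16 = 50.9. The standard error is √(2 × [(1120 − 50.9) / 50 + 50.9 / 42.5]) = 6.72.
- Ratio: 7.26 / 6.72 = 1.08. Simulation, which also carries the error of estimating the prediction, gives 7.33 and 6.78, again a ratio of 1.08.

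**4. Bias when loss depends on the POD2 score.** 4,000 simulated trials per scenario; true effect 22.5; logistic loss of POD7 with slope 1 per SD of the POD2 score, the same in both arms. The all-scores estimate regresses POD7 on the earlier scores with an intercept for each arm. It stands in for the mixed model: when only the last score can be missing and slopes are common to the arms, both give the same maximum-likelihood point estimate. Ranges are across independent runs.

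| Loss, placebo / ketamine | Deletion | All scores |
|---|---|---|
| 22% / 15% | 20.7 to 20.9 | 22.4 to 22.6 |
| 30% / 21% | 20.3 to 20.5 | 22.4 to 22.6 |

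The shrinkage is 22.5 − 20.9 = 1.6 to 22.5 − 20.3 = 2.2 points, or 7% to 10% of the effect. With the slope reversed, deletion gives 20.8 to 21.0, again toward zero. With lighter loss (about 10% and 7%) it gives 21.6. With no true effect, the mean estimate after deletion is 0.03 and false positives are not inflated.

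**The case against.** A reader might infer that the plan prescribes a complete-case analysis. It does not. Deletion is the default behaviour of the named method; the text gives no model form, software or handling of gaps, and a repeated-measures model fitted to one record per visit would keep partial data. This stands as a limit on the wording, but a plan that is silent on the matter does not avoid the default.

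A reader might also infer that the early scores are thrown away. They are not lost to the report: descriptive statistics by treatment are planned for all data, each questionnaire has its own ANOVA, and the Mann-Whitney route, if run visit by visit, needs no complete record. That route is reserved for non-normal data, however, and is not a missing-data rule. What is lost is the early scores' contribution to the planned treatment comparison.

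A third tempting reading is that deletion could create a false benefit. The modelled cases do not support it: the bias is toward no effect and is absent when the true effect is zero. That result assumes that loss depends on the score in the same way in both arms.

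Finally, the size is assumed and modest. Losing 15% to 30% of patients within seven days may prove pessimistic, and a bias of 1.6 to 2.2 points is about 0.2 to 0.3 of a standard error of 7.3. The simulation also favours the all-scores analysis by design, because loss depends on an observed score. If loss depended on the unseen POD7 score itself, neither analysis would be fully protected. These points stand, and they set the weight of the finding.

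**Conclusion.** The point holds as a cheap improvement. The plan names a method whose standard form needs complete records, states no analysis set or missing-data rule, and collects its last score by telephone from nearly everyone. Under the assumed loss, deletion shrinks a true effect of 22.5 to about 20.3 to 20.9, where all scores give about 22.5. With 15% lost at random, it raises the standard error from about 6.8 to about 7.3. These sizes rest on SD 40, correlation 0.6 and loss rates that the documents do not supply, so they show direction and order of magnitude only. The exposure is mainly POD7, and it applies to each questionnaire's own comparison.

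**What to change.** In the Statistical Analysis text, in both places where it appears, replace the repeated-measures ANOVA for the questionnaires with a likelihood-based mixed model for repeated measures: treatment, visit and treatment-by-visit, with an unstructured covariance. Include every randomised, dosed patient with at least one post-infusion score, analysed by randomised arm. State that scores collected before withdrawal or loss of contact stay in the analysis. Name the visits that enter for each questionnaire, since VAS is taken daily in hospital and the number of scores varies with length of stay. Recording the date and reason of withdrawal by arm would help readers judge the assumption below.

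The cost is SAP wording and slightly more analysis work; no extra patients or visits are needed. The downside is reliance on a missing-at-random assumption, which is still weaker than the one that deletion makes.

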This is a randomized, double-blind, placebo-controlled, two-arm parallel, single-center study. One hundred subjects (50 in each arm) will be enrolled. Subjects, between the ages 18 and 65, undergoing laparoscopic gastric bypass or sleeve gastrectomy under general anesthesia will be screened for eligibility to participate in the study. Subjects will be screened, recruited and consented during the preadmission visit prior to surgery. Eligible subjects will be randomized to one of the two treatment group in a 1:1 ratio to receive either IV ketamine (0.4mg/kg) or matching placebo. Both men and women will be recruited, and there is no limitation as to racial and ethnic origin.

Participation in the study will not alter the patient's surgical or anesthetic care, post-anesthetic care, or care on the floor. In the PACU, patients, if deemed medically stable by the study physician, will receive either 0.4mg/kg IV ketamine or placebo. All patients will also receive standard post-anesthetic monitoring and care, as well as routine care after transfer out of the PACU. There is no restriction on the use of other analgesics throughout the hospital stay. Patients are followed until the date of discharge, and endpoints (see below) are collected from patient reports as well as from medical charts. During their hospital stay (and once after their discharge from the hospital), patients will fill out five questionnaires which provide estimates of their postoperative pain control, mood and function, and quality of postsurgical recovery.

Patients will be randomized using a block randomization code for assigning 100 subjects to two groups. In Excel we generated 100 random numbers. In the next column we inserted multiple copies of the sequence PCPC where p= "placebo" and c = "control", forming 25 blocks. Then we sorted the random numbers in each 4 subject block, including the assignment letters (P, C) in the sort. The remaining list of Ps and Cs is the randomization.

To check the balance, we then did running counts of the cumulative repeats of "p" and "c" and "p - c". The tally for each totaled 50 and the two groups were always within 2 counts of being perfectly balanced, which met our goal. The list can be extended at will to accommodate screening failures.

Randomization lists will be sent to the pharmacy who will then be able to distribute the study drug/placebo as patients are enrolled and undergoing surgery, and the remainder of the study staff will be blinded.

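### Planned operation (bypass or sleeve) is neither a randomisation stratum nor a model term, so the valid unadjusted comparison gives up whatever precision it could provide

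*Combined protocol and SAP*

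**What the plan says.** **Population.** Overall study design and plan takes in both operations; candidates are those "undergoing laparoscopic gastric bypass or sleeve gastrectomy under general anesthesia will be screened for eligibility". The inclusion criteria under Study population also admit either one. No expected mix is given.

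**Randomisation.** The same design section says "Patients will be randomized using a block randomization code for assigning 100 subjects to two groups", built as 25 blocks of four with no stratification factor. The balance check covers arm totals only: "The tally for each totaled 50 and the two groups were always within 2 counts of being perfectly balanced".

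**Analysis.** Statistical Analysis, which appears a second time with the same content in the Data Safety and Monitoring Plan, gives the main method: "Analysis of variance (ANOVA) test with repeated measures will be performed to determine within-patient effects (time) and between patient effects (treatment) on outcome measures". Non-normal data go to Kruskal-Wallis and Mann-Whitney tests without strata. An exploratory logistic regression names no procedure covariate. Descriptive statistics are promised for subgroups where needed, but procedure is not named and a descriptive table does not adjust an arm comparison.

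**The concern.** The planned operation is part of the eligibility definition and is fixed before the infusion in the PACU, so it is a legitimate pre-treatment covariate. Pain, opioid use, time out of bed, length of stay and quality of recovery all follow from surgery, so it is plausible that they differ between two operations.

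If they do, the between-operation difference sits in the residual variance of every unadjusted comparison, standard errors are larger than they need be, and some power is lost. The planned power is about 0.80 with no dropout allowance stated, so there is little to spare. Deciding on adjustment only after the arms have been compared would also be a discretionary choice, which prespecification avoids.

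**Working it through.** **Inputs from the documents.** 50 per arm (Overall study design and plan); SD about 40%, detectable difference 22.5%, alpha 0.05, power 0.8 (Sample Size Justification). Standardised difference: 22.5/40 = 0.5625 SD.

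**Reproducing the plan's figure.** Two-sided, n per arm = 2(1.960 + 0.842)²/0.5625² = 49.6, rounded up to 50. Power at n = 50 is 0.803 by the normal formula and 0.795 by the noncentral t. The stated sample size is therefore sound. The t-based 0.795 is the reference below.

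**Assumptions.** The documents do not give the share π having one operation or the difference δ between operations (in within-procedure SDs). I take π from 0.1 to 0.5 and δ from 0 to 0.8.

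**Variance explained.** R² = π(1−π)δ² / [1 + π(1−π)δ²].
- δ = 0: R² = 0 for any mix.
- π = 0.1, δ = 0.8: 0.0576/1.0576 = 5.4%.
- π = 0.5, δ = 0.5: 0.0625/1.0625 = 5.9%.
- π = 0.5, δ = 0.8: 0.16/1.16 = 13.8%.

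**Power after adjustment.** With procedure in the model, the standardised difference becomes 0.5625/√(1−R²). Noncentral t, 50 per arm:

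| Mix | δ = 0 | δ = 0.5 | δ = 0.8 |
|---|---|---|---|
| 10:90 | 0.795 | 0.804 | 0.817 |
| 30:70 | 0.795 | 0.815 | 0.843 |
| 50:50 | 0.795 | 0.819 | 0.851 |

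At the most favourable corner (50:50, 0.8 SD), the normal formula gives the planned power with 43 per arm instead of 50.

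**Chance imbalance.** With 100 patients, 50 per arm and a fixed number having one operation, the count in one arm is hypergeometric. The chance that the arms differ by 20 points or more in procedure share is 7% at 50:50, 5% at 30:70, 2% at 20:80 and 0.1% at 10:90.

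**What such an imbalance would do.** Take a 20-point gap, δ = 0.5 and a 50:50 mix. The within-procedure SD is 40 × √(1 − 0.0588) = 38.8, so the estimate moves by 0.2 × 0.5 × 38.8 = 3.9 percentage units. That is 17% of the 22.5% design difference. The standard error of the unadjusted difference is 40 × √(2/50) = 8 units, so the shift is about half a standard error.

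**The case against.** The strongest reply is that nothing here is wrong with the plan. Under 1:1 randomisation the unadjusted comparison is unbiased and keeps its type I error. Its standard error already contains the between-operation variation, so chance imbalance is already paid for. All of that stands. A reader might infer that an imbalance in operations would bias the ketamine effect; the design does not support that. To list imbalance as a threat in addition to lost precision would count one thing twice.

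A reader might also infer that the operation is a known predictor, with length of stay and opioid use most affected. The documents do not say so. They report no outcome difference between the operations, and Outcome measures gives one typical discharge window, POD 2 or 3, for all patients. That is why the range above starts at zero and includes lopsided mixes.

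Third, BDI, MADRS and QoR-15 have preoperative scores, so a change-from-baseline or time-by-treatment contrast would remove stable differences between the two groups of patients on those scales. This stands in part: the plan names no such contrast, it would not remove an effect of the operation on postoperative change, and VAS and McGill have no preoperative score.

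Finally, other covariates could be proposed on similar grounds. That is fair, and it limits the weight of the point. The operation does have the advantage of being written into eligibility and available for every patient.

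**Conclusion.** The point holds as a minor, nearly free improvement, not as an error. Both operations are enrolled, and neither the list nor any planned test takes account of which one a patient has. The price is lost precision, of unknown size: 0% to 14% of variance and 0 to about 5.5 points of power (0.851 − 0.795 = 0.056), if the operations differ by 0 to 0.8 SD and the mix lies between 10:90 and 50:50. These ranges are assumptions. If the operation does not predict the outcomes, almost nothing is gained.

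It would go too far to conclude that the randomisation list has to be replaced. Once procedure is in the model, a stratified list adds little at this sample size.

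**What to change.** In both copies of Statistical Analysis, prespecify planned procedure (bypass or sleeve, as recorded before surgery) as a fixed factor in the between-arm models. Where a rank test is used, specify a van Elteren test stratified by procedure. The cost is one degree of freedom and a sentence in each place; no new data are needed beyond the planned operation. Separate blocked lists by procedure for patients not yet randomised are optional: they add minor pharmacy bookkeeping, and the fix does not depend on them.

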Ketamine, given for postoperative pain control, can be hypothesized to have long lasting analgesic effects as well as effects on improving mood and function in the postoperative period. Ketamine can be administered as a single dose in the post-anesthetic care unit (PACU), where patients are closely monitored for potential side effects. We hypothesize that postoperative use of ketamine should lead to improvement in pain indices including visual analog scale (VAS), a decrease in opioid requirement, mood improvements as measured by psychometric indices, and finally improvements in functional measures including early mobility and faster discharge from the hospital. In addition, we will assess serum levels of IL-1, 6, TNF- α , and BDNF to see if alterations in levels of cytokines and neurotrophic factors occur with postoperative pain and how ketamine treatment may influence the levels of these biomarkers.

Study Objective

Specific aim 1: examine the effect of a single, subanesthetic dose (0.4mg/kg) of ketamine vs. saline control on mood and postoperative function in patients who have undergone gastric bypass and sleeve gastrectomies.

Pain relief and changes in postoperative mood and function will be assessed using both patient report, in the forms of a series of questionnaires, and medical chart review. The questionnaires we use will be Beck Depression Inventory (BDI), Visual Analog Scale (VAS), McGill's short form, QoR-15 form and the Montgomery-Asberg Depression Rating Scale (MADRS). Please see below for a detailed discussion of these forms. In addition, from the chart review we will monitor length of stay during hospitalization, opioid usage per hour during the PACU stay before and after ketamine infusion, total opioid usage per day throughout the hospital stay, time to out of bed to chair, and spirometry use after ketamine infusion.

Specific aim 2: examine the effect of a single, subanesthetic dose (0.4mg/kg) of ketamine vs. saline control on inflammatory cytokines and neurotrophic factors in the postoperative period.

We will examine the effect of ketamine on proinflammatory markers and neurotrophic factors known to be linked with pain. We will examine levels of interleukin factor 1 and 6 (IL-1, IL-6), TNF- α , and BDNF. This aim will provide potential mechanism of action for ketamine.

Overall study design and plan

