Length of stay, opioid usage, and anti-emetic use will be recorded from electronic medical chart. Patient will be asked to record and report the time to OOB. Spirometry use will be assessed by a study team member to determine whether the patient is meeting the goal set by the surgical team 4 hours after ketamine infusion.

Exploratory secondary outcome measures: changes in serum levels of IL-1, IL6, TNF- α , and BDNF, which will be collected at baseline (in the OR preoperatively), and 15 min and 4 hours after the termination of ketamine infusion.

Study population

Inclusion criteria:

1. Adults, >18 years, <65 years, who will undergo gastric bypass or sleeve gastrectomy.
2. Subject is non-lactating and is either:
 - a. Not of childbearing potential; or
 - b. Of childbearing potential but is not pregnant at time of baseline as determined by pre-operative pregnancy testing.
3. Subject is ASA physical status 1, 2, or 3.
4. Subject who is deemed medically stable

Exclusion criteria:

1. <18 years of age; >65 years of age
2. Pregnant or breastfeeding
3. Does not speak or understand English (the study forms used are copy-right in English)
4. Cognitively impairment (by history) or clinical signs of altered mental status
5. History of misuse or abuse of ketamine
6. History of chest pain or chest pain in the PACU
7. Use of a medication that interferes with metabolism of ketamine within the last 24 hours
8. A diagnosis of schizophrenia and/ or a history of chronic antipsychotic medication use
9. History of head trauma
10. History of intracranial mass or hemorrhage
11. History of stroke
12. History of cardiac arrhythmia
13. Subject for whom ketamine is contraindicated
14. Unwillingness to give informed consent according to HIC guidelines

Entry into Study

Flyers will be designed and posted in the bariatric clinic as well as the pre-admissions testing (PAT) clinic to inform patients about this study. Patients will be recruited from the bariatric clinic during their visit with the pre-surgical clinic visit with their surgeons, from the PAT during their preadmission visit, or from the holding area on the day of surgery. Researchers will hold a general discussion with interested patients regarding the study. The patient may have family included, if he/she prefers. We will be approaching all subjects (male and female) who are undergoing laparoscopic gastric bypass or sleeve gastrectomy.

Pre-Study Screening

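### BDI, MADRS and QoR-15 have a baseline that the repeated-measures ANOVA gives no stated role; naming it as a covariate gains precision at almost no cost

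*Combined protocol and SAP*

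**What the plan says.** Under Outcome measures, after consent in the pre-admission clinic, "patients will be asked to fill out BDI, MADRS and QoR-15 forms to establish baseline scores". The first two scales are scored again on the day of surgery: "The BDI, MADRS will be filled out on postoperative days (POD) 0 after the infusion of ketamine". The schedule for the later days covers all three scales: "BDI, MADRS and QoR-15 forms will be repeated on POD1, 2 and 7". So BDI and MADRS have one baseline and four post-infusion scores, and QoR-15 has one baseline and three. All three are listed as primary outcomes.

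The Statistical Analysis section, repeated in the Data Safety and Monitoring Plan, gives one model for repeated outcomes, an ANOVA that "will be performed to determine within-patient effects (time) and between patient effects (treatment) on outcome measures". It names no covariate, no change score and no treatment-by-time interaction, and does not say whether baseline is a time level. The absolute and percent differences mentioned there are descriptive and are not tied to baseline.

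Three other places bear on the point:

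- Study Objective: "Pain relief and changes in postoperative mood and function will be assessed using both patient report". The word for change would allow a change-from-baseline reading.
- Exploratory secondary outcome measures: the serum markers "will be collected at baseline (in the OR preoperatively), and 15 min and 4 hours after the termination of ketamine infusion", so they too have a pre-treatment value.
- Entry into Study: patients may be recruited "from the PAT during their preadmission visit, or from the holding area on the day of surgery". The last route could leave a patient without baseline forms.

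**The concern.** The trial measures a baseline for a stated purpose, and the analysis gives it no role. Three readings are open, and two analysts could follow the plan and run different tests.

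1. *Baseline is a time level.* The treatment main effect is then averaged with a visit at which randomization makes the expected arm difference zero.
2. *Only post-infusion visits enter.* The baseline goes unused.
3. *Change from baseline is analysed.* This adds noise when baseline and later scores correlate weakly.

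None of these is baseline as a covariate. At stake is the power of the treatment test on three primary scales. VAS and McGill are outside the point, because the study schedule sets no pre-infusion score for them.

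**Working it through.** **Plan's own figure.** Sample Size Justification gives 50 per arm, SD 40%, a detectable difference stated as "our outcome variable of $\pm 22.5\%$ with a probability (power) of 0.8", and alpha 0.05 (taken as two-sided). The standard error is 40 × √(2/50) = 8.0, and 22.5/8.0 = 2.81. Power is 0.803 by the normal approximation and 0.795 by the t-test. The figure reproduces.

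**Set-up.** In a balanced repeated-measures ANOVA, the treatment main effect is a t-test on each patient's mean over the time levels. Let k be the number of post-infusion visits (4 for BDI and MADRS, 3 for QoR-15), d the average post-infusion effect with visits weighted equally, *a* the correlation between post-infusion visits and *b* the correlation between baseline and a post-infusion visit. The documents give neither *a* nor *b*, so both are assumed. With equal visit variances and complete data, in units of the single-visit variance:

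| Analysis | Effect | Variance |
|---|---|---|
| Baseline as level | d·k/(k+1) | (k²v + 1 + 2kb)/(k+1)² |
| Post-infusion only | d | v = (1+(k−1)a)/k |
| Change from baseline | d | v + 1 − 2b |
| Baseline as covariate | d | v − b² |

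**Dilution.** 22.5 × 4/5 = 18.0% (BDI, MADRS); 22.5 × 3/4 = 16.9% (QoR-15). The biomarkers, with one pre-treatment and two later samples, would have 2/3. For a common correlation a = b = ρ from 0 to 0.7, the lower variance brings the net standardized effect back to 0.89 falling to 0.81 of the post-only value (k = 4), and 0.87 falling to 0.76 (k = 3).

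**Worked case, BDI/MADRS, a = b = 0.5, single-visit SD 40%.**

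- Level: variance (16 × 0.625 + 1 + 4)/25 = 0.60; SE 40 × √0.60 × √(2/50) = 6.20; 18.0/6.20 = 2.90; power 0.82.
- Post-only: v = (1 + 1.5)/4 = 0.625; SE 6.32; ratio 3.56; power 0.94. Change has the same variance here.
- Covariate: 0.625 − 0.25 = 0.375; SE 4.90; ratio 4.59; power 0.995.

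**Common correlation 0.1 / 0.3 / 0.5 / 0.7, single-visit SD 40%, effect 22.5%** (noncentral t, 98 df, 97 if adjusted):

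| Analysis | BDI, MADRS | QoR-15 |
|---|---|---|
| Level | 0.99 / 0.92 / 0.82 / 0.72 | 0.96 / 0.86 / 0.75 / 0.66 |
| Post-only | 0.998 / 0.98 / 0.94 / 0.89 | 0.99 / 0.97 / 0.93 / 0.88 |
| Change | 0.75 / 0.85 / 0.94 / 0.995 | 0.72 / 0.82 / 0.93 / 0.99 |
| Covariate | 0.999 / 0.99 / 0.995 / 0.999 | 0.99 / 0.99 / 0.99 / 0.999 |

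**Separate correlations.** Baseline is taken before surgery and the other scores within a week after it, so *b* may be lower than *a*. With a = 0.7 and b = 0.2, BDI/MADRS variances are v = (1 + 2.1)/4 = 0.775; level (12.4 + 1 + 1.6)/25 = 0.60; covariate 0.775 − 0.04 = 0.735. Power for level / post-only / covariate is 0.82 / 0.89 / 0.90. For QoR-15 it is 0.78 / 0.88 / 0.89. The ranking holds and the gain is much smaller.

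**Other meanings of the 40% SD.** If it is the SD of the post-infusion mean, then over a common correlation of 0.1 to 0.7 the level analysis has power 0.67 to 0.61 (BDI, MADRS) or 0.64 to 0.56 (QoR-15), post-only 0.795 throughout, and the covariate analysis 0.81 to 0.996 or 0.805 to 0.99. If it is the SD of a single-visit change, then at ρ = 0.7 BDI/MADRS power for level / post-only / change / covariate is 0.51 / 0.69 / 0.94 / 0.98.

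**Typical effect of 40%.** With baseline as a level, the lowest power over a common correlation of 0.1 to 0.7, with 40% as either the single-visit SD or the SD of the post-infusion mean, is 0.965.

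**False positives.** Simulation of normal data with a common correlation (5,000 trials per setting) gave type I error of 0.044 to 0.056 over the four analyses.

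**The case against.** The plan is silent about baseline; it does not exclude it. The 4/5 and 3/4 fractions belong to one of three readings, and before the variance offset. A treatment-by-time interaction would not be diluted, though the plan names none. The size of the gain rests on unknown correlations, and adjusted powers near 0.99 need baseline to predict the postoperative scores well. At the typical effect the plan cites, even the diluted test has ample power. All of this stands, and it limits the point to precision and clarity.

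A reader might infer that the trial is underpowered as designed, or that its sample size is wrong. The documents do not support that: 50 per arm reproduces, and whether power falls below 0.80 depends on the reading, the correlations, the meaning of the SD and the true effect. A reader might also infer inflated false-positive risk from the handling of baseline. None of the four analyses shows it.

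It can also be said that a covariate does not settle everything. The covariance structure, the missing post-infusion scores and the weighting of visits still need a decision; the equal weights used here are a choice, not something the documents fix. That stands, but it does not weaken the case for giving baseline a role.

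**Conclusion.** The point holds as a low-cost improvement. The plan collects a baseline for three primary scales and does not say how it is used. Entered as a time level, it cuts the treatment main effect to 4/5 or 3/4, which nets to about 0.81–0.89 or 0.76–0.87 of the post-only standardized effect for a common correlation of 0 to 0.7. The covariate analysis was at least as powerful as each alternative at every positive correlation tried; at zero correlation it gains nothing and costs one degree of freedom.

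How much it gains cannot be fixed from the documents. For BDI/MADRS at a 22.5% effect and single-visit SD 40%, the advantage over post-only ranges from about 0.05 in power (0.94 to 0.995, all correlations 0.5) to about 0.015 (0.886 to 0.901, post-post 0.7 and baseline-post 0.2). These figures assume equal variances, complete data, normal scores and equal visit weights.

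**What to change.** In both copies of the statistical text (Statistical Analysis, and its repeat in the Data Safety and Monitoring Plan), state for BDI, MADRS and QoR-15:

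- The outcomes are the post-infusion scores (BDI and MADRS: POD 0, 1, 2, 7; QoR-15: POD 1, 2, 7), in a repeated-measures model with treatment, visit, treatment-by-visit and the pre-surgery score as covariate. Baseline is not a time level.
- The treatment test is the average post-infusion difference. By-visit differences are reported with 95% confidence intervals.
- A missing baseline score is mean-imputed, blind to arm, so that patients recruited in the holding area are kept. With an assumed 20% of baselines missing at random, adjusted power with single-visit SD 40% stays at 0.98 or more over a common correlation of 0.1 to 0.7.
- This model remains the main treatment test for the three scales even if scores are non-normal, with Mann-Whitney as a supportive analysis. Otherwise the existing rule for non-normal data would move them to an unadjusted rank test.

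Apply the same adjustment to the biomarkers, using the preoperative sample. Keep the existing ANOVA sentence only for the remaining repeated outcomes, such as daily opioid use, VAS and McGill.

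Cost: wording in two places, a little programming and one degree of freedom. No new data, visits or patients.
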